The study will be performed with an Investigational Device Exemption (IDE). The investigational device provided will have met design controls per FDA code of federal regulation (CFR): 21 CFR 820.30. Endolumik Inc. will serve as the industry sponsor for this study and will donate the devices being used for the protocol to the two participating study sites. Development of the technology in this research is supported by the West Virginia University Department of Surgery.

Scientific rational with References:

Background on Morbid Obesity, Bariatric Surgery & Sleeve Gastrectomy

More than one-third of U.S. adults (42%) and 17% of U.S. children and adolescents have obesity. The CDC projects that an even larger proportion of the population will suffer from obesity by 2030, and if current trends continue, >57% of today's youth will have obesity at age 35 [1]. In addition, the World Health Organization has reported that global obesity rates have nearly tripled since 1975. Currently 39% of adults worldwide have an overweight body size and 13% have obesity [2]. The estimated annual medical cost of obesity in the U.S. was \$270 billion in 2011. Medical costs for individuals with obesity were \$1,429 higher than those with normal weight.

Bariatric surgery has emerged as the most effective treatment for obesity and obesity-related comorbidities. The use of bariatric surgery in the United States has increased from 150,000 operations in 2011 to 252,000 in 2018 [3]. However, less than 1% of patients who are eligible for bariatric surgery receive this care. Since 2013, the laparoscopic sleeve gastrectomy (LSG) has overtaken gastric bypass (RNY) as the most widely performed procedure in both community and academic practices [4].

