3. Participant Demographic Data
 - o Participant ID (assigned as described above)
 - o Study Site
 - o Date of Operation
 - o Surgeon

- o Operation Type
- o Patient Name
- o Medical Record Number
- o Age
- o Sex
- o Height
- o Preoperative Weight
- o Preoperative Body Mass Index (BMI)
- o Past Medical History (hypertension, hyperlipidemia, diabetes, asthma, obstructive sleep apnea, emphysema/COPD, gastroesophageal reflux disease, chronic kidney disease, heart disease, liver disease, venous thromboembolism)
- o Past Surgical History

4. Outcome Data

- o Operative time (minutes)
- o Intraoperative adverse events
- o 30-day morbidity/MBSAQIP Occurrences
- o Device Evaluation Form(s)
- o Video file of operation

How will the results be analyzed?

Descriptive statistics will be calculated for the patient cohort.

Data Monitoring Committee & Data Monitoring Plan

The plan for monitoring data to ensure subject safety (e.g. serious adverse event and unanticipated problem reporting) includes the creation of the following: a formal multidisciplinary Data Monitoring Committee (DMC), a schedule for the DMC to meet, as well as a list of device-related complications that will be monitored for during and after each use of the device.

The Data Monitoring Committee will consist of the following four members: [name] MD, [name] MD, and [name] MBA. The multidisciplinary Data Monitoring Committee (DMC) will meet at regular intervals to ensure no serious adverse events or unanticipated problems arise during device testing, specifically the DMC will meet to review intraoperative outcomes after every 5 patients, and immediately after any adverse events.

Data Monitoring Committee Members

1. **[name] MD, MMM, FASA** is an anesthesiologist and the medical director of Perioperative services for WVU Medicine Children's Hospital. She has more than 30 publications, with several funded studies. She was part of WVU Health Sciences Office of Research Integrity and Subject protection- Institutional Review Board from 2014-2021 and has been a part of numerous study approvals and its review including medical devices. She is also an integral part of the

Children's Hospital Research Consortium which will oversee all research and quality projects at WVU Medicine Children's Hospital.

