2. **[name] MD** obtained her medical degree at Indiana University School of Medicine and completed surgical residency at Ascension Providence Hospital / Michigan State University in Southfield, Michigan. She then completed a Minimally Invasive Surgery Fellowship at the University of California San Diego. Her research interests include clinical outcomes and global health.
3. **[name] MBA** is the Chief Executive Officer of Endolumik Inc. She is a mechanical engineer and seasoned medical device executive, with experience launching medical devices for Johnson & Johnson and Philips Healthcare.

Collection, Assessment and Reporting of Adverse Events

The most important goal of our team during this pilot study is to ensure the safety of the device being tested.

The two adverse events which will signal an immediate end to the study are: (i) if the device leads to an intraoperative perforation of the esophagus or stomach or (ii) if the device is stapled across. If these events were to occur, the study would be ended and a root cause analysis would be performed.

The protocol for recording, reporting and remediating adverse events will be as follows: Following each device use, the clinical providers (surgical team, anesthesia team, operating room staff/nurse) will complete a de-identified web-based questionnaire (Device Evaluation Form). Included in this questionnaire is an area to report any adverse event occurrence. Furthermore, if an intraoperative adverse event occurs, the operating surgeon will notify the study PI immediately following the operation; the PI will arrange for a meeting of the Data Monitoring Committee so that the adverse event can be discussed and a remediation plan can be developed.

Risk to participants:

The risks to participants include the risks of elective surgery which are bleeding, infection, damage to surrounding structures, need for further operations, venous thromboembolism, stroke, heart attack, or death. Furthermore, the potential adverse events associated with bariatric surgeries may include leaks, strictures, ischemia, gastroesophageal reflux disease, chronic pain, dysphagia, and excess weight loss.

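### The sponsor's chief executive sits without restriction on the only safety-review committee in a first-in-human study of the sponsor's own device

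*Combined protocol and SAP*

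**What the plan says.** The section *Data Monitoring Committee & Data Monitoring Plan* makes the DMC part of the plan for subject safety. It opens the membership list with "The Data Monitoring Committee will consist of the following four members", and three entries follow: two physicians and one person with an MBA. Under *Data Monitoring Committee Members*, item 3 says that the last of these "is the Chief Executive Officer of Endolumik Inc".

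The committee is to "meet at regular intervals to ensure no serious adverse events or unanticipated problems arise during device testing". On timing, "the DMC will meet to review intraoperative outcomes after every 5 patients, and immediately after any adverse events". Under *Collection, Assessment and Reporting of Adverse Events*, after an intraoperative adverse event the principal investigator convenes the DMC "so that the adverse event can be discussed and a remediation plan can be developed". The same section states: "The most important goal of our team during this pilot study is to ensure the safety of the device being tested".

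The *Lay Summary* describes a first-in-human study and says: "Endolumik Inc. will serve as the industry sponsor for this study and will donate the devices being used for the protocol". The *Sample Size Justification* places the study ahead of a 510(k) application. The device description adds that the company holds an exclusive licence to the underlying intellectual property.

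**The concern.** A safety committee is useful because its members can read the emerging data without a stake in the answer. Here one member leads the company that developed the device, holds the licence, sponsors the study and plans to seek clearance. That member has an interest in how outcomes are interpreted, whether an event is attributed to the device, and which remediation is chosen.

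Much of the committee's work is judgement. No comparison group is described, the analysis is descriptive, and apart from two study-ending events no numerical safety criterion is given. Bleeding and infection appear under *Risk to participants* both as risks of surgery and as complications of calibration tubes, so attributing such an event to one or the other is a matter of interpretation.

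The concern is with interpretation and response. Clinical providers record the events, so the raw record is not in question. Nor are the two study-ending events, which are rules of the study and do not wait for a DMC decision.

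**Working it through.** The protocol gives no figure to reproduce on this point, and the finding rests on no power, alpha or event rate. The check sets the relevant sections side by side and counts the reviews.

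**Membership and limits**

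| Question | What the protocol gives | Where |
|---|---|---|
| Who sponsors the study and donates the device? | Endolumik Inc. | *Lay Summary* |
| Who is DMC member 3? | That company's chief executive | *Data Monitoring Committee Members*, item 3 |
| Is any other safety committee, medical monitor or adjudicator described? | No | Whole document |
| Is member 3 limited by observer or non-voting status, recusal or a closed session? | No | Whole document |
| Is a DMC charter or conflict-of-interest rule stated or named as an attachment? | No | Whole document |
| How many members? | Four stated, three listed | *Data Monitoring Committee & Data Monitoring Plan* |

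The chief executive is 1 of 3 listed members (33%), or 1 of 4 (25%) if the stated number is right. Without the chief executive, 3 − 1 = 2 listed members remain.

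**Reviews affected**

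Inputs: total sample size n of 20 to 30 (*Sample Size*), and one review per 5 patients (*Data Monitoring Committee & Data Monitoring Plan*).

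- Scheduled reviews, n/5: 20/5 = 4; 30/5 = 6.
- At these two sizes the last review follows the final patient. Reviews that come before further operations: 4 − 1 = 3; 6 − 1 = 5. Sizes between 20 and 30 also give 3 to 5.
- Participants still to be operated on after the first review, n − 5: 20 − 5 = 15 (15/20 = 75%); 30 − 5 = 25 (25/30 = 83%). This assumes that each review is held before the next operation, which the protocol does not say.

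Meetings after adverse events come on top of these. The chief executive is a member for all of them, with no exception stated.

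These counts show how often the committee can influence what follows. They would be the same under any membership and do not measure bias.

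**The case against.** The strongest case on the other side accepts the membership fact and disputes its weight.

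- **The role is inferred from silence.** No voting, quorum or decision rule is given for any member, and the protocol calls the committee formal and multidisciplinary, never independent. This is correct, so the document does not contradict itself. But the chief executive is listed as a member with nothing to set the role apart, and that absence of a limit is the finding.
- **The remit is narrow.** Scheduled meetings cover intraoperative outcomes, 30-day morbidity is not named for them, and no authority to stop or continue is assigned to the DMC. Two device-specific events end the study by rule. This stands and reduces the consequence. It leaves the DMC with the other adverse events, whether the device led to a perforation, and the remediation plan.
- **The sponsor classes the study as non-significant risk** (*Device Risk Determination*). That bears on how much oversight is proportionate. It is the sponsor's own determination, and it does not settle a conflict inside a committee that the protocol chose to create for subject safety.
- **Other features limit the risk.** Several providers report after each operation, 30-day outcomes follow a listed set of occurrences, two of the three listed members are physicians, and there are no unblinded comparative data to protect. These protect the record more than its interpretation.
- **Device knowledge is needed when remediation is discussed.** Item 3 describes an engineer with device experience. The point is fair, and the proposed change keeps that input in an open part of the meeting.

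**Conclusion.** The concern holds. As written, the plan places the head of the sponsor, without any stated limit, on the only body that reviews safety in a first-in-human study of the sponsor's device. That covers 4 to 6 scheduled reviews, 3 to 5 of them before further operations, plus any meeting prompted by an adverse event. The practical effect cannot be quantified from the documents. It is moderated by the narrow remit and by the two study-ending rules.

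The conclusion assumes that no document outside the protocol already restricts this member's role; none is named. If one exists, a single line citing it would resolve the point. The change should be made, but it is a matter of governance wording and does not undermine the study. The mismatch between four stated and three listed members is a minor, separate error and adds nothing to the conflict.

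**What to change.** Amend the DMC membership text in three respects.

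1. State that the sponsor's chief executive is a non-voting attendee who supplies device information and then leaves the meeting.
2. State that conclusions on outcomes, adverse events and remediation are reached only by members whom the sponsor does not employ.
3. Reconcile the number of members: list the fourth if one has already been appointed, otherwise correct the count.

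The study-ending events stay as written.

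The cost is a wording change, with no new member, visit or data. There are two downsides. If no fourth member has been appointed, only two people reach the conclusions. The sponsor's device knowledge is also available only in the open part of the meeting.

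The change removes the sponsor's direct role and does not make the committee fully independent. Member 1 holds a post at WVU Medicine, and the *Lay Summary* says: "Development of the technology in this research is supported by the West Virginia University Department of Surgery". Member 2's current affiliation is not stated.

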The current pilot protocol is a qualitative, not quantitative, study design, thus no power calculation is indicated. The goal of the present pilot study is to serve as the First In Human IDE trial and confirm that the Endolumik Gastric Calibration Tube performs similar to predicate devices currently on the market, as well as to get end-user feedback prior to 510(k) application to the FDA. The sample size was chosen because 20 to 30 uses will allow the development team to appropriately evaluate device performance.

Study Design and Procedures

1. The study type is prospective and non-randomized.
2. The sample size will be 20-30 Bariatric patients (total between both testing sites) who meet the inclusion criteria listed above.
 - a. Twenty participants meeting inclusion criteria will undergo laparoscopic or robotic sleeve gastrectomy using the Endolumik Gastric Calibration Tube instead of the standard bougie calibration tube. This bariatric operation will take approximately 60 minutes. The amount of time the Endolumik Gastric Calibration Tube will be inside the patient is approximately 20 minutes. The device is removed prior to the conclusion of the operation, while the patient is under anesthesia.

The portions of the sleeve gastrectomy operation where the Endolumik Gastric Calibration Tube will be used include:

- ***To evacuate gastric contents***
- ***During construction of the gastric sleeve***
- ***To perform the leak test of the gastric sleeve***

b. Ten participants meeting inclusion criteria will undergo laparoscopic gastric bypass using the Endolumik Gastric Calibration Tube instead of the standard calibration tube. This bariatric operation will take approximately 120 minutes. The amount of time the Endolumik Gastric Calibration Tube will be inside the patient is approximately 20 minutes. The device is removed prior to the conclusion of the operation, while the patient is under anesthesia.

The portions of the gastric bypass operation where the Endolumik Gastric Calibration Tube will be used include:

- ***To evacuate gastric contents***
- ***During construction of the gastric pouch***
- ***To calibrate closure of the gastrojejunal anastomosis***
- ***To perform a leak test of the gastrojejunal anastomosis***

3. Eligible participants will undergo informed consent.

4. The operative steps for use of the Endolumik Gastric Calibration Tube during the sleeve gastrectomy operation are as follows:

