- f. Prior to placing ports, a skin incision will be made with a scalpel for each port site. Access to the peritoneum will be gained using an optical trocar in the left upper quadrant.
- g. The remaining ports will be placed under direct laparoscopic visualization: a 12mm port in the left supraumbilical area, one 5mm port in the right upper quadrant, and one 15mm port in the right supraumbilical area.
- h. A liver retractor will be placed through a 5mm epigastric incision.
- i. Under laparoscopic visualization with the laparoscopic camera in NIR mode the Endolumik Gastric Calibration Tube, which will be sitting at 30cm in the esophagus, will be advanced by the head of bed provider under direct visualization of all team members (anesthesia team at head of bed and surgical team in sterile field) into the stomach and connected to suction to evacuate gastric air and contents. Once the gastric contents are removed, the Endolumik Gastric Calibration Tube will be taken off suction, visualized using NIR camera mode, and withdrawn to the top gastroesophageal junction.
- j. During creation of the gastric pouch, with the surgical camera in NIR mode, the Endolumik Gastric Calibration Tube will be advanced into the stomach to assist with pouch size calibration and pouch size measurement.
- k. During creation of the gastrojejunostomy, the Endolumik Gastric Calibration Tube will be advanced through the gastrojejunal anastomosis calibrate closure and prevent narrowing of said anastomosis.
- l. Once the gastrojejunostomy is completed the the Endolumik Gastric Calibration Tube will be used to perform a leak test. The accessory bulb will be connected to the the Endolumik Gastric Calibration Tube and inflated to the pressure of 35mm Hg. A bowel clamp will be placed on the roux limb distal to the gastrojejunostomy. The gastrojejunostomy will be submerged in saline and evaluated for any leak.
- m. The Endolumik Gastric Calibration Tube will be removed under direct visualization.
- n. The surgeon will perform an intraoperative upper endoscopy to examine the gastric pouch mucosa and the gastrojejunostomy anastomosis.
- o. The gastric bypass operation will be completed in standard fashion.

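### Study-ending criterion (i) covers only the esophagus and stomach, but in bypass the tube also passes through the gastrojejunal anastomosis, so a jejunal-side perforation gets discretionary review and no automatic stop

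*Combined protocol and SAP*

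**What the plan says.** The section Collection, Assessment and Reporting of Adverse Events gives a closed list, opening with "The two adverse events which will signal an immediate end to the study are". Criterion (i) applies "if the device leads to an intraoperative perforation of the esophagus or stomach". Criterion (ii) is that the tube has been stapled across. The consequence is fixed: "If these events were to occur, the study would be ended and a root cause analysis would be performed".

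Other intraoperative adverse events take a different route. The surgeon tells the principal investigator straight after the operation, and the investigator convenes the DMC "so that the adverse event can be discussed and a remediation plan can be developed". The Data Monitoring Committee & Data Monitoring Plan section also has the committee meet "immediately after any adverse events".

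In Study Design and Procedures, item 2b lists four uses of the tube in bypass, one of which is "To calibrate closure of the gastrojejunal anastomosis". Item 5, step k, describes that use: "the Endolumik Gastric Calibration Tube will be advanced through the gastrojejunal anastomosis calibrate closure and prevent narrowing of said anastomosis".

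**The concern.** The hard stop is tied to named organs, and the planned path of the tube in bypass goes past them. As written, what follows a perforation caused by the tube depends on where along that path it occurs. In the esophagus or stomach, the study ends and a root cause analysis is done. A short distance further on, at the jejunal side of the join, there is a committee meeting and a remediation plan. The committee may itself stop the study, but that is a judgement made after the event and not a rule fixed beforehand. In a first-in-human study whose stated priority is device safety, a serious injury caused by the device is the kind of event for which a rule set in advance is preferable.

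**Working it through.** No formula applies and the plan states no figure to reproduce. The check sets the stopping rule against the operative steps and then counts exposure.

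**Applying the rule, case by case**

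| Event caused by the tube during surgery | Criterion (i) | Criterion (ii) | Consequence as written |
|---|---|---|---|
| Esophageal or gastric perforation | Met | – | Study ends, root cause analysis |
| Tear on the gastric pouch side of the anastomosis | Arguably met (pouch is stomach) | – | Study ends, root cause analysis |
| Tube stapled across, at any site | – | Met | Study ends, root cause analysis |
| Jejunal-side perforation, tube not stapled | Not met | Not met | Immediate DMC review, remediation plan |

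Only the last row is a gap. No other section extends criterion (i) to the jejunum or the anastomosis.

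**Which steps take the tube past the stomach**

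- Sleeve (item 2a): 0 of 3 listed uses. All three are gastric.
- Bypass (item 2b): 1 of 4 listed uses, namely step 5k.
- The bypass leak test, step 5l, is not counted. It says "A bowel clamp will be placed on the roux limb distal to the gastrojejunostomy", but not that the tube crosses the join.

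**Exposure** (Sample Size section: 20 sleeve and 10 bypass participants, total 20 to 30)

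- Bypass share at full enrolment: 10/30 = 33%.
- Bypass participants if all 20 sleeves are done: from 20 − 20 = 0 to 30 − 20 = 10.
- Further bypass participants whose treatment would rest on the DMC's decision after an event in the first bypass: at most 10 − 1 = 9. This is an upper bound, because the committee may stop.

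**Cost of a wider rule at full enrolment**

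- Event in the very first participant: 30 − 1 = 29 planned participants not treated (9 bypass and 20 sleeve).
- Event in the last participant: 0.
- The order of enrolment is not stated, so the range is 0 to 29.

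**The case against.** The organ list is not arbitrary. The background section gives esophageal and gastric perforation, and stapling of the tube, as the typical injuries. Risk to participants repeats these among the known complications of all calibration tubes and says that the study device shares them. Keeping the hard stop for recognised harms and leaving the rest to a committee is a legitimate design choice. No document describes a jejunal perforation caused by a tube, and step 5k gives no depth of insertion beyond the join. All of this stands. It explains where the list came from, but those lists concern calibration tubes in general and do not address the extra path in bypass.

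The event is also already handled: it is reported at once and the DMC meets. That stands too. A reader might infer that such an injury could go unrecorded or unreviewed, and the documents do not support that. What is missing is only the automatic consequence. The fallback is discretionary, and one listed DMC member is the sponsor's chief executive. That implies no misconduct, but it is a reason to prefer a fixed rule here.

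A third objection is that a wider rule would end the whole study, including the sleeve group, which never undergoes step 5k. True, but the protocol already accepts exactly that for a gastric perforation in a bypass patient.

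Finally, naming the whole anastomosis as a stopping site would invite dispute. At an unfinished join, device injury may be hard to tell from suture or staple failure. This stands, and the fix below is limited accordingly.

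**Conclusion.** The gap is real and narrow. A jejunal-side perforation caused by the tube, without stapling, triggers immediate DMC review but neither an automatic end to the study nor a root cause analysis. It can arise only in bypass participants, up to 10 of 30, and only at step 5k. These counts measure exposure to a step, not risk.

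Two stronger readings are tempting. One is that any injury at the anastomosis escapes the stopping rule; it does not, since a pouch-side tear is arguably gastric and a stapled tube meets criterion (ii). The other is that the sponsor gave no thought to the sites; the list visibly follows the protocol's own injury lists, and whether the jejunum was left out on purpose is not stated.

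The conclusion assumes that a tube passed through the join from the gastric side reaches the jejunal side. Attachments not shown, such as the evaluation forms, may name bowel injury for monitoring, but the protocol fixes the study-ending events at two. No endpoint or analysis is affected. This is a point for the sponsor to consider, not a serious defect.

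**What to change.** Extend the sites in criterion (i) to: esophagus, stomach (including gastric pouch) or jejunum (including the jejunal side of the gastrojejunal anastomosis). Keep the existing condition that the device must have caused the perforation. Add one sentence stating that suture- or staple-line leaks not caused by the tube go to the DMC and do not end the study.

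This needs a few words in one section and no new procedure, data field or participant. The price is a small added chance of ending the study early, sleeve group included. It is called small on the assumption that the injury is rare, because the protocol does not list it among typical tube injuries; no rate is given. Some judgement about cause at the join will remain, which the added sentence limits but does not remove.
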